1.0 TRIAL SUMMARY & SCHEMA

Abbreviated Title	Embr Wave Study
Trial Phase	Feasibility
Clinical Indication	Patients with a breast cancer history experiencing bothersome hot flashes
Trial Type	Feasibility Pilot Trial
Type of control	Non-placebo controlled
Route of “administration”	Wrist, non-invasive wearable thermoelectric system
Trial Blinding	no
Treatment Groups	Two-arm, cross-over, non-placebo controlled trial
Number of trial subjects	50
Estimated enrollment period	12 months
Estimated duration of trial	Patients will not be followed after study termination
Duration of Participation	Approximately 8 weeks

1.1 Trial Design

This study is a randomized, crossover, non-placebo controlled trial of 50 patients with history of breast cancer and bothersome hot flashes. We propose to have 25 patients per arm in a two-arm study randomized to Embr Wave device vs no device or other treatment for bothersome hot flashes with a 1-month crossover. *The study has enrolled 23 participants with no active subjects in follow up as of 01/05/2022. The current amendment version dated 1/5/2022 includes the following changes a) update the study intervention to recently launched Embr Wave Generation 2 device and b) enroll an additional 10 participants so that approximately 50% of the study population will use the Generation 2 device. This increases initial planned sample size of n=40 by an additional 10 subjects to n=50. Study design shown below in Figure 1.*

[Type here]

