1.1 Primary Objective

- (1) To evaluate the feasibility of using EMBr Wave technology in women with a history of breast cancer who are experiencing bothersome hot flashes.

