3.2 EMBr Wave Device

While there are non-hormonal medical options to treat hot flash for breast cancer survivors, this study is investigating the use of a personalized cooling mechanism for hot flash relief. The EMBr Wave device has not previously been tested in clinical studies in breast cancer, but shows novel and promising hot flash relief for this unique population, possibly allowing for hot flash reduction without the use of an oral medication. The EMBr Wave device (both Generation 1 and 2) works by delivering heating or cooling pulses through the wrist bracelet. Because of the wrist's sensitivity to temperature, these pulses can be used to promote overall comfort despite other uncomfortable temperature sensations affecting the entire body. Users simply press either the cooling or heating button depending on which sensation they desire. The Generation 2 Embr Wave device has the same functionality as the Generation 1 device, but with an improved smaller design. A graphical design of the devices is shown in Figure 2.

[Type here]

Figure 2: EMBR Wave Generation 1 Device (top) and Embr Wave Generation 2 Device (bottom)

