3.3 Rationale and Feasibility

There are multiple side effects associated with breast cancer treatments, which are unable to be treated with traditional hot flash symptom management due to the contraindication of HRT in women who have been diagnosed with breast cancer. Safe and affordable strategies that may aid in the management of debilitating hot flashes are therefore needed. The overall objectives of this pilot trial are to evaluate a promising non-invasive intervention for treatment of hot flashes via EMBR Wave. If data from this pilot evaluation suggest that Embr Wave is beneficial, then more formal studies, with larger patient numbers, will be considered. Our goal is to leverage these results to secure additional funding, from grants or commercial partners, to support larger pilots and/or the development of new prototype devices.

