4.4 Hot Flash Assessments

This pilot trial will be conducted to get an initial reading as to the potential benefit of EMBr Wave for diminishing distress caused by hot flashes. We do not expect that this instrument will

[Type here]

actually decrease the number of hot flashes. However, it might decrease hot flash severity and decrease the interference of hot flashes on patients' lives. The main instrument to determine the amount that hot flashes are interfering with patients' lives is by using a validated instrument called the Hot Flash-Related Daily Interference Scale (HFRDIS).³

Additionally, we will follow daily hot flash numbers and severities. The hot flash number and severity will be measured by the Daily Hot Flash Score,⁴ which is a composite entity of both frequency and severity of hot flashes. The Daily Hot Flash Score is computed by the grade of severity multiplying the frequency of the same grade hot flashes according to the hot flash diary over a 24 hour period.

The OCEAN survey will also be administered to the participant to complete at baseline. This survey assesses the participant's personal connectedness that they have with their body and to the world around them. This survey gives perspective to the information obtained from the participant while they are using the EMBr Wave.

Patients will also be given instructions on how to sync their EMBr Wave with the EMBr Wave mobile application once a day, which will allow us to collect usage data from the devices. This will be used to further understand technology adoption over the 4 weeks that patients are using EMBr Wave during study participation.

We will also evaluate patient satisfaction with device use at the end of treatment using a 10-point Likert scale and through answering several Likert-type questions related to perceived device efficacy. These items will include assessment of the ways EMBr Wave had the greatest potential efficacy, such as reduction in hot flash severity, frequency, duration, sense of control, or self-esteem, as well as device usage.

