12.0 STATISTICAL CONSIDERATIONS

12.1 Statistical Data Analysis and Study Design

Feasibility will be evaluated primarily with respect to device usage, and secondarily with respect to patient satisfaction. Device usage will be evaluated by the number of minutes and sessions per 24-hour day per participant. The mean patient satisfaction scores for each Likert-type question and proportion of reporting satisfaction scores at or above 7 will be estimated in the entire sample and compared between sequence groups at the 5% significance level (two-sided).

Preliminary efficacy will be evaluated with respect to the Hot Flash-Related Daily Interference Scale (HFRDIS), hot flash number and severity (as a daily hot flash score; DHFS), and patient perception of efficacy (10-point Likert scale items). HFRDIS measurements will be evaluated at the end of each week on the study, and DHFS will be used as recorded in the daily hot flash journal. Repeated measurements will be modeled as repeated outcomes in a linear mixed effects model with fixed effects for treatment, period, and treatment-by-period interaction, and random effects for subjects and for subject-by-treatment interactions to account for correlated measurements within the same subject. The period variable will be represented in the sum-to-zero coding so that the target of inference will be the fixed main effect of treatment, tested at the 5% significance level (two-sided). Thus the treatment effect will be interpreted as time-averaged and estimated using information from the mixed model. Patient perception of efficacy will be evaluated at the end of the device period and estimated in the entire sample and compared between sequence groups.

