All analyses will proceed on an intent-to-treat basis. When observations of preliminary efficacy endpoints are missing, the rest of that patient's observations may still be used in the mixed effects model. To assess the potential impact of informative loss to follow-up, we will compare patients who leave the study or cease reporting endpoints to those who provide data for the full study duration. Patients will be compared on the basis of baseline variables and available longitudinal measurements. The pattern of loss to follow-up will be reported via CONSORT chart. Potential impact on estimates will be assessed via multiple imputation. For the purpose of evaluating compliance, patients who leave the study will be recorded as not wearing the device after leaving the study, ensuring that all patients are evaluable.

As an exploratory analysis, individual components of the HFRDIS will be analyzed using the same model as the total HFRDIS. As sensitivity analyses, the preliminary efficacy analyses will be repeated allowing for temporal correlation of measures, and including as covariates any baseline variables with large imbalances.

Our feasibility target is that at least 75% of all patients meet the compliance criteria described above. The minimum number of the 38 enrolled patients meeting the compliance criteria to achieve this threshold is 23 (77%), in which case the 95% Jeffreys interval lower bound is 60% (thus we can rule out population compliance rates below 60%) (Figure 3, left). We expect the population compliance rate to be at least 85%, in which case we have at least 93% probability of

[Type here]

achieving the compliance target (Figure 3, right). With a population compliance rate of 80%, we have a 76% probability of achieving the compliance target.

[figure not shown]

Figure 3: **Left:** Jeffreys intervals (95% equal tail probability credible intervals from a Beta(0.5, 0.5) prior) corresponding to various sample proportions with 30 patients. **Right:** Probability of achieving target compliance rate for various population rates.

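### Does section 12.1 need a planned summary by device generation, given that the sample was enlarged so that about half would use Generation 2?

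*Combined protocol and SAP*

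**What the plan says.** Section 1.1 (Trial Design) reports 23 patients enrolled and none in active follow-up on 5 January 2022. It replaces the device with Generation 2 and adds 10 patients to the planned 40. The only reason given for the addition is to "enroll an additional 10 participants so that approximately 50% of the study population will use the Generation 2 device".

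Section 3.2 says the newer device has the "same functionality as the Generation 1 device, but with an improved smaller design".

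The primary objective (under section 2.0) is "To evaluate the feasibility of using EMBr Wave technology in women with a history of breast cancer" and bothersome hot flashes. Neither it nor the secondary objectives mention generation.

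Section 12.1 sets the analyses:
- Usage: "Device usage will be evaluated by the number of minutes and sessions per 24-hour day per participant".
- Feasibility target: "at least 75% of all patients meet the compliance criteria described above".
- Satisfaction and perceived efficacy: estimated in the whole sample and compared between sequence groups.
- Efficacy: a mixed model with treatment, period and their interaction as fixed effects.

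None of these refers to generation, and section 4.3 does not stratify randomization.

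**The concern.** A sample size is normally raised to serve a planned estimate or test. Here it was raised to reach a device mix, yet no output is broken down by that mix.

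The one stated difference between the devices is size. For something worn on the wrist day and night, size could plausibly affect how long it is worn and how well it is liked, and these are the two feasibility measures. The documents give no evidence on whether it does.

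Section 4.4 says usage data will be "used to further understand technology adoption over the 4 weeks" of wear, and section 3.3 hopes the results will help "support larger pilots and/or the development of new prototype devices". For either purpose a reader would want to know how the current model performed. A pooled rate could hide a lower rate on Generation 2, and a split chosen only after the data are seen carries less weight than one planned beforehand.

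**Working it through.** **Inputs.** 23 patients enrolled before the change; planned sample 40, then 50 (section 1.1). Compliance target 75%; benchmark of 23 compliant patients, 77%, lower bound 60% (section 12.1). Assumption: the first 23 all used Generation 1 and everyone later uses Generation 2.

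**1. The share.** Without the addition: (40 − 23)/40 = 17/40 = 42.5%. With it: (50 − 23)/50 = 27/50 = 54%. This agrees with the stated figure of about 50%.

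**2. Precision of a Generation 2 compliance rate.** Jeffreys 95% limits are the 2.5% and 97.5% points of Beta(x + 0.5, n − x + 0.5).

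| Compliant / n | Rate | 95% interval | Width |
|---|---|---|---|
| 23/30 (plan's benchmark) | 76.7% | 59.6% to 88.9% | 29 points |
| 13/17 (Generation 2 within 40) | 76.5% | 53.3% to 91.5% | 38 points |
| 21/27 (Generation 2 within 50) | 77.8% | 59.8% to 90.2% | 30 points |

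The first row reproduces the plan's 77% and 60%. It does so at n = 30, although the text says 38 patients; that mismatch is a separate matter and does not affect this point. For a satisfaction mean, the half-width t(0.975, n − 1)/√n falls from 0.51 SD (n = 17) to 0.40 SD (n = 27).

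**3. Precision of a comparison.** With 85% compliance in both generations, the half-width of the difference is 1.96 × √[0.85 × 0.15 × (1/23 + 1/27)] = 0.199, about 20 points. At 80% in both it is 0.222. Generation also coincides with enrolment before or after the amendment, so a difference could not be put down to the device.

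**4. Can the pooled verdict hide a poor Generation 2 result?** Take a pooled threshold of 38/50 (0.75 × 50 = 37.5, rounded up), 85% compliance on Generation 1, and an illustrative Generation 2 mark of 21/27 (0.75 × 27 = 20.25, rounded up). With X1 ~ Bin(23, 0.85) and X2 ~ Bin(27, p), P(X1 + X2 ≥ 38 and X2 < 21) is:
- p = 0.90: 1.2%
- p = 0.85: 7.7%
- p = 0.80: 20.7%

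In all three cases the true Generation 2 rate is above 75%, so a pooled pass is correct and a count below 21 is sampling noise. A single outcome, 20/27 (74.1%, one patient short), supplies 5.2 of the 7.7 points and 11.5 of the 20.7. These figures show how easily a split would mislead; they do not show a hidden failure.

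Real masking needs a true Generation 2 rate below 75%. At p = 0.70 the true pooled rate is (23 × 0.85 + 27 × 0.70)/50 = 38.45/50 = 76.9%, and P(X1 + X2 ≥ 38) = 63.7%. A pass is still the right answer for all patients taken together. An interval some 30 points wide on 27 patients could not reliably separate 70% from 75% either.

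**The case for a change.** The strongest case for a change is that the device mix is the sole stated reason for 10 more patients; power, drop-out and pooled precision are not mentioned. If generation had no bearing on anything reported, that reason would be empty. The closest existing analysis, the sensitivity model with imbalanced baseline covariates, covers efficacy only and does not name generation. The addition would cost two sentences and one table, and at 27 patients the Generation 2 interval is about as wide as the plan's own benchmark interval.

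Much of this stands. The omission is real, and a short descriptive table would be sensible in the report.

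Two parts do not stand. First, a target share need not imply a subgroup analysis. It may serve to make the pooled result reflect the device now on the market, and a pooled rate with 27 of 50 patients on Generation 2 does reflect that mix. The documents do not say which purpose was meant, and they set no precision goal for either generation. Second, prior specification protects tests and decisions. The table in question would have neither, so planning it in advance protects little. Its compliance row could not be filled in yet anyway, because the supplied text does not contain the compliance criteria to which section 12.1 refers.

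**Conclusion.** No change to the plan is needed. Followed as written, section 12.1 gives a valid feasibility verdict on the stated objective, and pooling fits the description of the two devices as functionally the same. A split by generation would alter no primary, secondary or safety conclusion. It would give one descriptive table on about 23 and 27 patients, with roughly 30-point intervals for each rate and about a 20-point half-width for the difference, and it would be inseparable from calendar time.

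Analysts can produce that table when reporting. Usage and satisfaction are already collected for each patient, and generation follows from enrolment before or after the amendment if the presumed clean switch holds. If reported, it should be labelled descriptive and not read as a comparison of devices.

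The group sizes rest on the presumed 23/27 split. The compliance illustrations also rest on a 38/50 threshold and on assumed true rates. The conclusion would differ if generation were named in an objective or decision rule, or if the documents held evidence that the smaller design changes wear; neither is the case.

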1.2 Study Schema

[figure not shown]

Figure 1: Study schema

2.0 TRIAL OBJECTIVES

This study will evaluate the preliminary efficacy of the EMBr Wave wrist device in managing the symptoms of hot flashes in patients with a history of breast cancer who have been experiencing hot flashes for at least 30 days prior to study entry. This study is based on published data that this device can improve thermal comfort by producing varying temperature pulses to counter uncomfortable sensations of heat or coolness.

1.1 Primary Objective

- (1) To evaluate the feasibility of using EMBr Wave technology in women with a history of breast cancer who are experiencing bothersome hot flashes.

1.2 Secondary Objectives

- (1) To evaluate the preliminary efficacy of EMBr Wave in reducing hot flash severity and frequency in women with a history of breast cancer.
- (2) To identify in what ways EMBr Wave has the greatest potential efficacy, such as reduction in hot flash severity, frequency, duration, sense of control, or self-esteem.
- (3) To estimate effect sizes to inform power calculations for a future Phase III trial

[Type here]

[figure not shown]
3.0 BACKGROUND

3.1 Bothersome Hot Flashes

At menopause, roughly 75% of women report bothersome hot flashes.¹ While the gold standard for hot flash relief is Hormone Replacement Therapy (HRT), this treatment is contraindicated for women with a history of, or active, breast cancer. Simultaneously, due to the negative impact of chemotherapeutics on remaining endogenous estradiol levels, and/or the induction an earlier menopause, breast cancer survivors often report more severe hot flash compared to women without breast cancer, negatively affecting their quality of life (QOL).²

3.2 EMBr Wave Device

While there are non-hormonal medical options to treat hot flash for breast cancer survivors, this study is investigating the use of a personalized cooling mechanism for hot flash relief. The EMBr Wave device has not previously been tested in clinical studies in breast cancer, but shows novel and promising hot flash relief for this unique population, possibly allowing for hot flash reduction without the use of an oral medication. The EMBr Wave device (both Generation 1 and 2) works by delivering heating or cooling pulses through the wrist bracelet. Because of the wrist's sensitivity to temperature, these pulses can be used to promote overall comfort despite other uncomfortable temperature sensations affecting the entire body. Users simply press either the cooling or heating button depending on which sensation they desire. The Generation 2 Embr Wave device has the same functionality as the Generation 1 device, but with an improved smaller design. A graphical design of the devices is shown in Figure 2.

[Type here]

Figure 2: EMBR Wave Generation 1 Device (top) and Embr Wave Generation 2 Device (bottom)

3.3 Rationale and Feasibility

There are multiple side effects associated with breast cancer treatments, which are unable to be treated with traditional hot flash symptom management due to the contraindication of HRT in women who have been diagnosed with breast cancer. Safe and affordable strategies that may aid in the management of debilitating hot flashes are therefore needed. The overall objectives of this pilot trial are to evaluate a promising non-invasive intervention for treatment of hot flashes via EMBR Wave. If data from this pilot evaluation suggest that Embr Wave is beneficial, then more formal studies, with larger patient numbers, will be considered. Our goal is to leverage these results to secure additional funding, from grants or commercial partners, to support larger pilots and/or the development of new prototype devices.

4.0 METHODOLOGY

4.1 Entry Criteria

4.1.1 Inclusion Criteria

In order to be eligible for participation in this trial, the subject must:

1. Age \geq 18 years.
2. Women with history of breast cancer, DCIS, or LCIS (currently without evidence of malignant disease)
3. Bothersome hot flashes (defined by their occurrence of \geq 28 times per week and of sufficient severity to prompt the patient to seek therapeutic intervention). Mean severity in a day should be \geq 4/10 on log scale of 0 (none at all)-10 (extremely).
4. Presence of hot flashes for $>$ 30 days prior to study entry
5. Ability to complete questionnaire(s) by themselves or with assistance.
6. Willingness to wear EMBR Wave device during the study period

[Type here]

7. Willingness to use the EMBr Wave mobile application
8. Have a working smartphone that can download the EMBr Wave mobile application (iPhone 6 or more recent generation, Android 8.0 or more recent generation)
9. ECOG Performance Status (PS) = 0, 1
10. Ability to provide informed written consent.
11. Life expectancy ≥ 6 months

4.1.2 Exclusion Criteria

Any of the following current (≤ 4 weeks prior) or planned therapies:

1. Antineoplastic chemotherapy (anti-HER2 agents allowed)
2. Androgens
3. Systemic estrogens. Local vaginal estrogen preparations are allowed, but need to have been initiated for vulvo-vaginal atrophy at least 28 days prior, and must not be expected to stop or change the dose or frequency of the medication during the study period.
4. Progestogens
5. Tamoxifen, raloxifene and aromatase inhibitors are allowed, and must not be expected to stop the medication during the study period
6. SSRIs/SNRIs, when being used for hot flash management or other indications such as depression, is allowed, assuming the dose will remain unchanged for the study duration
7. Gabapentin/pregabalin, is allowed, assuming the dose will remain unchanged for the study duration
8. Clonidine
9. Prior use of EMBr Wave.
10. Nickel allergy
11. Pregnant or nursing women since the safety of device has not been established in this population

4.2. Study Location and Sample

This study will be open for accrual at the Stefanie Spielman Comprehensive Breast Center and James Cancer Hospital. This trial will be conducted under the auspices of The Ohio State University. Testing will take place in clinics of the Stefanie Spielman Comprehensive Breast Center or done so virtually via phone and/or video calls. Patient eligibility will be determined according to the eligibility criteria listed. The study will enroll up to approximately 50 patients.

4.3 Registration and Randomization

Subjects who have given informed consent will be registered by the research coordinator and given a study number. Subjects will then be randomized via block randomization with random block sizes by the study coordinator following a randomization schedule produced by the statistician. Randomization will not be stratified.

4.4 Hot Flash Assessments

This pilot trial will be conducted to get an initial reading as to the potential benefit of EMBr Wave for diminishing distress caused by hot flashes. We do not expect that this instrument will

[Type here]

actually decrease the number of hot flashes. However, it might decrease hot flash severity and decrease the interference of hot flashes on patients' lives. The main instrument to determine the amount that hot flashes are interfering with patients' lives is by using a validated instrument called the Hot Flash-Related Daily Interference Scale (HFRDIS).³

Additionally, we will follow daily hot flash numbers and severities. The hot flash number and severity will be measured by the Daily Hot Flash Score,⁴ which is a composite entity of both frequency and severity of hot flashes. The Daily Hot Flash Score is computed by the grade of severity multiplying the frequency of the same grade hot flashes according to the hot flash diary over a 24 hour period.

The OCEAN survey will also be administered to the participant to complete at baseline. This survey assesses the participant's personal connectedness that they have with their body and to the world around them. This survey gives perspective to the information obtained from the participant while they are using the EMBr Wave.

Patients will also be given instructions on how to sync their EMBr Wave with the EMBr Wave mobile application once a day, which will allow us to collect usage data from the devices. This will be used to further understand technology adoption over the 4 weeks that patients are using EMBr Wave during study participation.

We will also evaluate patient satisfaction with device use at the end of treatment using a 10-point Likert scale and through answering several Likert-type questions related to perceived device efficacy. These items will include assessment of the ways EMBr Wave had the greatest potential efficacy, such as reduction in hot flash severity, frequency, duration, sense of control, or self-esteem, as well as device usage.

The HFRDIS, Daily Hot Flash Score, and OCEAN survey will be administered on paper or virtually via RedCap survey distribution at baseline. Participants will be given paper Daily Hot Flash Score sheets for their own use. For study data collection, electronic surveys will be sent by email via Research Electronic Data Capture (REDCap) for daily and weekly hot flash assessments and the post-treatment satisfaction and efficacy questionnaires. Survey reminder emails and phone calls from study team will be sent to participants for incomplete HFRDIS surveys and satisfaction and efficacy assessments. If a participant initiated the daily surveys on paper prior to the study team using electronic data collection, she will continue using paper assessments for the duration of the study. If assessments are incomplete at end of intervention, the study coordinator will utilize paper forms to collect assessments, as appropriate.

Virtual enrollment will be presented as an option to eligible participants. In this option, calls (phone and/or video) will be done between the research coordinator and participant to discuss the study; screen for eligibility; discuss the informed consent and how to sign it; orient the patient to the device and associated smart phone application; and discuss how to return the device at the conclusion of the device usage. The informed consent document will be sent to the participant to sign via email or mail to obtain a pen signature after the participant has verbally agreed to participate in the study during the call. In addition to either receiving the signed informed consent form via email or mail, the participant will also be able to email the full picture of their signed informed consent form to the study coordinator's email and this will serve as a third option of informed consent documentation. After the consent document is signed, randomization will be done and the research coordinator will then inform the patient the

[Type here]

next steps depending upon their group assignment. When it is time for the participant to wear the device, it will be mailed to them via a secure and reliable address. An orientation call will be conducted when the device is received and will be worn starting the day of their designated month. The device will be returned at the end of this said month. For the orientation call, the participants will be sent an instructional packet to reference and discuss. These participants that enroll virtually will also complete the surveys electronically via RedCap. The EMBr device will be mailed in safe and secure packaging for transit.

The OSUCCC Recruitment, Intervention and Survey Shared Resource (RISSR) will be utilized to administer electronic data collection for assessments. REDCap (Research Electronic Data Capture) provides a secure, web-based application that is flexible enough to be used for a variety of types of research, provides an intuitive interface for users to enter data and has real time validation rules (with automated data type and range checks) at the time of entry. Data are maintained behind the OSUMC firewall, and REDCap is 21 CFR Part 11 capable. It offers easy data manipulation with audit trails and ad hoc reporting functionality for reporting, monitoring and querying patient records, and an automated export mechanism to common statistical packages (SPSS, SAS, Stata, R/S-Plus).

